## 5. INVESTIGATIONAL PRODUCT AND TREATMENT OF SUBJECTS

### 5.1 Investigational Products [IP]

#### 5.1.1 Test Product

The test product is Permethrin Cream 5% w/w manufactured by Mayne Pharma International Pty Ltd., supplied in 60 g tubes. The formulation composition of the test product consists of the following ingredients:

**Active Ingredient** - Each gram contains permethrin 50 mg (5%).

**Inactive Ingredients** - Fractionated coconut oil (MCT-NF) [7.5%], Isopropyl myristate NF [0.8%], Glyceryl monostearate NF [2.0%], Lanolin alcohols NF [0.2%], Mineral oil NF [0.01%], Butylated hydroxytoluene NF (BHT) [2.4%], Polyoxyethylene 2 cetyl ether (ceteth 2) [2.4%], Polyoxyethylene 10 cetyl ether (ceteth 10) [2.4%], Glycerol NF [0.5%], Water USP [74.96%], Polyoxyethylene 20 cetyl ether (ceteth 20), [2.0%], Carbomer 974P NF [0.26%], 5% NaOH Aqueous solution [1.6%], Formaldehyde solution NF [0.27%].

#### 5.1.2 Reference Product/Comparator

The reference product or comparator is Elimite™ marketed by Prestium Pharma, Inc. ("Prestium"), the branded subsidiary of Renaissance Pharma. Elimite™ is supplied in 60 g tubes. The formulation composition of the reference product, Permethrin 5% w/w (Elimite™) consists of the following ingredients according to the FDA-approved labelling:

**Active Ingredient** - Each gram contains permethrin 50 mg (5%).

**Inactive Ingredients** - Butylated hydroxytoluene, carbomer homopolymer type B, fractionated coconut oil, glycerin, glyceryl monostearate, isopropyl myristate, lanolin alcohols, mineral oil, polyoxyethylene cetyl ethers, purified water, and sodium hydroxide. Formaldehyde 1 mg (0.1%) is added as a preservative.

### 5.2 Standard of Care [SOC]

Generic Permethrin Cream, 5% available in the market will be supplied by the Sponsor in an open-label fashion as a Standard of Care (SOC) to each site and will be used for treatment of the household members. To avoid any possible unblinding issues, the SOC supplied by the Sponsor will not be the reference product of this study, Elimite™.

### 5.3 Packaging and Labeling

The investigational product tubes to be dispensed to the subject will be packaged in diaper-label to ensure

blinding. Labeling will be in accordance with Good Manufacturing Practice. The labels on each investigational product tube will not provide any information in regards to treatment arm.

The SOC, Permethrin Cream, 5% available in the market will be supplied in an open-label fashion.

#### **5.4 Storage of investigational product and SOC**

Study Medication supplies (include investigational product and SOC) will be stored at 20° to 25°C (68° to 77°F) and protected from moisture. All study medication supplies must be kept in a secure cabinet or room. Only the study pharmacist, or designated study personnel will have access to study medication supplies.

#### **5.5 Reserve Sample Retention**

Each shipment of investigational product received by the site will contain investigational product tubes to be reserved for retention. When the site receives a shipment of investigational product, study pharmacist, or designated study personnel will randomly select one block of the investigational product for retention and store them separately. For all subsequent shipments, the same procedure is to be followed. Detailed guidance is provided in the study *Pharmacy Manual*.

As per the Code of Federal Regulations Part 21, Section 320.38(e), "Each reserve sample shall be stored under conditions consistent with the product labeling and in an area segregated from the area where testing is conducted and with access limited to authorized personnel. Each reserve sample shall be retained for a period of at least 5 years following the date on which the application or supplemental application is approved, or, if such application or supplemental application is not approved, at least 5 years following the date of completion of the clinical study in which the sample from which the reserve sample was obtained was used."

The Investigator will store the retention sample investigational product until such time or until notification is received from the Sponsor that the samples are no longer required and proper instruction of what to do with the sample is given by the Sponsor.

#### **5.6 Treatment Assignment (Randomization)**

The block randomization code will be generated and held by an independent third party throughout the conduct of the study in order to minimize bias. Blocks of two (2) tubes will be supplied to the sites. Site's dispensing pharmacist will randomly select a tube with an investigational product from the block for the study subject. Next enrolled subject will receive the remaining investigational product from the same block until the block is entirely used.

##### **5.6.1 Assignment of Retreatment**

Based on the clinical judgement and requirements described in the protocol, the Investigator may provide

a retreatment to the study subject. Only one retreatment is allowed per subject. The retreatment assignment must belong to the same treatment arm. In order to dispense the correct treatment, the following process is to be followed:

1. Study pharmacist will contact the Drug Depot, specifying subject's identifying information.
2. Drug Depot will specify which kit number shall be dispensed for retreatment.

Please refer to the study *Pharmacy Manual* for details.

## 5.7 Blinding

This is a double-blind study, thus all clinic staff, study monitors, and subjects will be blinded to the randomization scheme. The packaging of the test and the reference products will be similar in appearance to make difference in treatment less obvious to the subjects. To maintain adequate blinding of Investigators and subject evaluators, it is recommended that the investigational product dispensation and accountability be performed by the study pharmacist, or designated study personnel who will not be involved in any other activities of this study. Neither the Investigator nor the patient should be able to identify the received treatment. The dispensed investigational product will NOT be opened by the subject at the study center. The randomization scheme will not be available to the physician, the study pharmacist or designated study personnel for investigational product dispensation and accountability and nursing staff or study coordinators involved in the collection, monitoring, revision, or evaluation of adverse events or to clinical staff who could have an impact on the outcome of the study.

A sealed copy of the randomization code will be supplied with each block of the investigational product and will be retained at each clinical site. Randomization codes must be available to the FDA or other regulatory agency investigators at the time of site inspection to allow for verification of the treatment identity of each subject.

The randomization code must not be broken except in emergency situations for which the identification of the study treatment of a subject is required by the Qualified Investigator to complete a serious adverse event report or the clinical report. In such situations, the randomization information will be held by designated individual(s), and the date and reason for breaking the blind must be recorded. Biorasi Project Manager should be contacted by telephone prior to unblinding but no later than 24 hours after unblinding. As the study is blinded, the Investigator should promptly document and explain to the Sponsor any premature unblinding (e.g., accidental unblinding, unblinding due to a serious adverse event) of the investigational product(s).

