## **7.6 Unblinding due to SAE**

Treatment assignment for an individual subject should be unblinded only in an emergency by the Investigator, when knowledge of the treatment assignment is urgently needed for the clinical management or welfare of the subject. Treatment should be provided in accordance with the medical condition and with regard to the information provided in the Investigator's Brochure.

The Investigator must document the breaking of the code, and the reasons for doing so on the eCRF, in the site file, and in the medical notes.

The Investigator must notify the Sponsor in writing as soon as possible following the code break detailing the necessity of the code break. Subject always to clinical need and where possible, all other members of the research team should remain blinded.

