From Day 1 through the end of the study, the randomization code must not be broken except in emergency situations for which the identification of the study treatment of a subject is required by the Qualified Investigator for subject safety and medical care. In the event of a medical emergency requiring identification of the study drug administered to an individual subject, Investigator will make every attempt to contact the Biorasi Project Manager by telephone, explaining the need for unblinding, before or no later than 24 hours of breaking the blinding. The Investigator must document the time, date, and reason for the unblinding and the names of the personnel involved on the CRF, in the site file, and in the medical notes. The Investigator must notify the Sponsor in writing as soon as possible following the unblinding event explaining the necessity of unblinding of the investigational product(s). Every effort should be made to avoid unblinding extra study personnel.

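### Protocol 5.7 gives completing a report as the purpose of an emergency code break, in conflict with Protocol 7.6 and SAP 3.3, and a sealed code per block of two can expose a second subject

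*Protocol*

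**What the plan says.** Three sections state when the blind may be broken.

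- **Protocol 5.7 (Blinding)** forbids breaking the code "except in emergency situations for which the identification of the study treatment of a subject is required by the Qualified Investigator to complete" one of two documents. The full purpose clause reads "required by the Qualified Investigator to complete a serious adverse event report or the clinical report".
- **Protocol 7.6 (Unblinding due to SAE)** says "Treatment assignment for an individual subject should be unblinded only in an emergency by the Investigator", and only "when knowledge of the treatment assignment is urgently needed for the clinical management or welfare of the subject".
- **SAP 3.3** follows the structure of the 5.7 sentence but ends it differently: identification must be "required by the Qualified Investigator for subject safety and medical care". It does not mention a report.

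On the physical code, Protocol 5.7 states "A sealed copy of the randomization code will be supplied with each block of the investigational product" and that the copy stays at the site; SAP 3.3 says the same. Protocol 5.6 states "Blocks of two (2) tubes will be supplied to the sites", with the remaining tube going to the next subject enrolled there. SAP 3.2 specifies 1:1 allocation in blocks of two, stratified by site.

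**The concern.** A site that consults 5.7 finds a documentation purpose for unblinding that 7.6 and SAP 3.3 do not give. Protocol 7.5 adds some pressure in the same direction: it lists study drug information among the minimum content of an SAE report due within 24 hours, although it does not ask for the unblinded treatment.

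The rule matters because the primary endpoint depends on an assessor's judgement. Healing of old lesions is judged by visual examination (Protocol 6.2.1.5), while new lesions are to be confirmed by microscopy (6.2.2.1). Protocol 7.6 has the Investigator break the code, and Section 6 asks that the same Investigator or site personnel assess subjects whenever possible. The person who learns an assignment may therefore be the person who later scores cure.

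The block-level code widens the exposure. Protocol 7.6 contemplates unblinding one subject. A code that covers a block of two can disclose the arm of the adjacent enrollee at the same site, who may still be under assessment. If the second tube is still in stock, it discloses the next subject's arm before enrolment, which is a failure of allocation concealment.

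**Working it through.** **1. The three purposes side by side**

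| Section | Emergency required? | Stated purpose | Unit |
|---|---|---|---|
| Protocol 5.7 | Yes | Complete an SAE report or the clinical report | A subject |
| Protocol 7.6 | Yes | Urgent clinical care or welfare | An individual subject |
| SAP 3.3 | Yes | Safety and medical care | An individual subject |

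All three require an emergency. They differ in purpose, and the purpose in 5.7 appears in neither of the others. Completing the clinical report is hard to regard as an emergency need at all.

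**2. The plan's own figures**

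The point disputes no sample-size figure, but enrolled N is the denominator below, so it was checked. Exact enumeration of two independent binomials with the Protocol 8.3.2 interval gives:

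- 56 per arm, 88% vs 88%: power 0.817 (stated at least 0.80); 56/0.8 = 70 per arm, 140 in total.
- 91 per arm, 86% vs 88%: power 0.952 (stated at least 0.95); 91/0.8 = 113.75, rounded up to 114 per arm, 228 in total.

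Both reproduce.

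**3. What one opening reveals**

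A 1:1 allocation in blocks of two puts one Test and one Reference tube in each block. The blocks needed for dispensing number 140/2 = 70, or 228/2 = 114 at the larger size.

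| Enrolled N | Intended, 1/N | Block code opened, 2/N |
|---|---|---|
| 140 | 0.71% | 1.43% |
| 228 | 0.44% | 0.88% |

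**4. How many openings**

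The documents give no code-break rate, so a range is assumed. At N = 140, openings = rate × 140:

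| Assumed rate | Openings | Assignments exposed, at most (2 × openings) |
|---|---|---|
| 0.5% | 0.7 | 1.4 |
| 1% | 1.4 | 2.8 |
| 3% | 4.2 | 8.4 |
| 5% | 7.0 | 14.0 |

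The last column is a ceiling, because two unblinded subjects may share a block. For k randomly chosen subjects the expected number exposed is N × [1 − C(N−2, k)/C(N, k)]. With k = 5 and N = 140 this is 140 × [1 − (135 × 134)/(140 × 139)] = 9.86, close to 10.

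**5. Would a code per subject restore the limit of one?**

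Not fully. In a fixed 1:1 block of two, knowing one tube's arm gives the other's by elimination to anyone who knows which two subjects shared the block. Protocol 5.6 states both the block size and the rule for the remaining tube, so sites have that information.

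**The case against.** The strongest reply is that 5.7 keeps the emergency condition. It also requires the date and reason to be recorded, the project manager to be telephoned, and any premature unblinding to be explained to the Sponsor. A reader might infer that 5.7 lets sites unblind routinely to complete paperwork; the text does not support that. It is also true that 7.6, the section dedicated to this situation, already holds the narrower rule, asks that the rest of the team stay blinded where possible, and is matched by SAP 3.3. This makes the conflict easy to resolve but does not remove it, since a site may consult 5.7 alone.

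On the sealed code, the layout is not described. Separate concealed panels per tube would show only one line, and the Pharmacy Manual may say more. Nor do the documents say that an emergency break uses the sealed site copy: they mention that copy in connection with inspection and, for emergencies, refer to designated individuals holding the information. The second disclosure is therefore possible rather than certain, though inference by elimination remains whatever the layout.

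Two further inferences are not supported. One is that unblinded subjects would be lost from the per-protocol population: neither the protocol nor the SAP definition lists unblinding as an exclusion, and exclusion would need a ruling that it was a major deviation affecting evaluation. The other is that code breaks will be common. The product is a topical cream applied at most twice, the protocol cites absorption limited to 0.5%, and no break rate is given.

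**Conclusion.** The conflict of purpose is in the current text and should be corrected. Protocol 5.7 ties an emergency code break to completing a report, whereas Protocol 7.6 and SAP 3.3 tie it to the subject's care and safety. This conclusion needs no assumption.

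The per-block code is a secondary weakness. One opening can reveal 2 of 140 assignments (1.4%) instead of 1 (0.7%), or 0.9% instead of 0.4% at 228. This rests on each block holding one tube of each arm, which follows from 1:1 allocation in blocks of two, and on the sealed block copy being what is opened and showing both tubes. Over an assumed break rate of 0.5% to 5%, about 1 to 7 openings would occur among 140 subjects. The likely number affected is small. The issue is the integrity of assessor blinding and allocation concealment; sample size, error rate and planned power do not change.

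**What to change.** 1. **Reconcile the purpose.** In Protocol 5.7, replace the report wording with the purpose already stated in 7.6 and SAP 3.3: an emergency in which that subject's care, safety or welfare urgently requires the treatment identity. Add that completing a report is not a ground for unblinding. Deleting the report words alone is not enough, because 5.7 would then state no purpose. The cost is a wording amendment.

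2. **Supply sealed codes per tube or subject number.** This removes the direct disclosure of the second assignment, at the cost of re-printing. Make the matching change to the per-block sentence in SAP 3.3.

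3. **Record the remaining limit.** Step 2 is a partial improvement: while blocks are fixed at two and sites know it, the partner's arm can still be inferred. Removing that inference would mean changing the block scheme, which would affect packaging and the selection of reserve blocks under Protocol 5.5. The sponsor would need to weigh that separately.

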## 5.8 Treatment Administration

### 5.8.1 Investigational Product Dispensation and Application

At visit 2 (Baseline or Day 1), subjects will receive the randomized treatment along with a Subject Diary (Appendix C. Subject Diary). Subjects will be instructed to bring the dispensed study medication (used tube of investigational product) along with the subject diary for visit 3 (day 7) for investigational product

accountability.

Each subject will be instructed (verbally and in form of written instructions) on proper application method, clothing and bedding disinfection requirements, subject diary completion, and general instructions regarding the study. Subjects will apply investigational product on Day 1 after leaving the study site.

Subjects will be instructed to cleanse with warm water (but NOT the hot bath due to risk of increased adsorption and increased risk of systemic adverse events) and a non-medicated soap and dry thoroughly. Nails should be clipped back and any debris must be removed prior to the application. Subjects will apply a thin layer of investigational product to the entire surface from the neck down to the soles and bottom of the feet (NOT including face and head). Subjects should pay special attention when applying cream to the areas between fingers and toes, under nails, wrists, armpits, skin surface of external genitalia, breasts and buttocks. The investigational product should be applied at bedtime and kept overnight for a minimum of 8 hours and a maximum of 14 hours before washing it off.

Subjects will be informed that residual itching may persist for several weeks after the successful treatment, which does not necessarily indicate treatment failure. Oral or topical antipruritics may be prescribed based on the Investigator's clinical judgement in order to reduce itching, taking into account prohibited medication and washout periods detailed in the Section 5.11.

In general, one application of the Permethrin is curative for scabies. However, in the event that signs of active scabies infestation are present at visit 4 (Day 14±2), the subject will be retreated with second application of their assigned investigational product. In this case, the subject will follow the same application recommendations and will complete the diary, returning the used investigational product tube and subject diary to the visit 5 (Day 28±4).

### **5.8.2 Administration of Standard of Care**

In the current study, all household members with prolonged physical contact with the subject must agree to be assessed by the Investigator. Affected (or "high risk") household members, as determined by the Investigator, must be willing to receive a treatment with an open-label standard of care, which will be provided to them on the day of visit 2 (baseline). Providing an antiparasitic treatment to the household members of the affected individual is dictated by the clinical and epidemiological necessity due to high risk of cross-contamination within the family members. Individuals receiving standard of care will not be considered as a part of study population.

All affected (or "high risk") household members must receive treatment with the standard of care on the same day as the enrolled subject and will follow the same recommendations for disinfection of personal clothing and bedding items. Please see Appendix A. Study Flowchart.

## **5.9 Treatment Compliance**

Subjects will apply the investigational product after the visit 2 (Day 1), preferably in the evening.

Subjects will be advised to bring back used investigational product tube during visit 3. The study pharmacist, or designated study personnel will perform investigational product accountability to ensure that the subject took application of the investigational product. Compliance with the application and disinfection requirements will be determined from the Subject Diary, which the subject will be instructed to use to record date and time of the application and application removal, as well as confirmation of disinfection of clothing and compliance of family members with SOC treatment.

Missed applications and deviations from the application instructions (e.g.: if cream was washed with soap and water within 8 hours of treatment, cream was not applied to the whole body during each application, was not performed prior to application of the investigational product, etc.) will be considered as a deviation from the protocol.

### **5.10 Accountability, Destruction and Return of Study Supplies**

The Sponsor will supply sufficient quantities of the investigational product for the following:

- (1) completion of this study
- (2) retention, as per applicable regulations

The study pharmacist or designated study personnel will maintain a Site Investigational Product Accountability Log and a Subject Investigational Product Accountability Log itemizing all investigational product dispensed to and returned from each subject during the study and the amount of SOC dispensed to the household members of each subject. Investigational product compliance check will be performed at visit 3 (Day 7) and at visit 5 (Day 28) - for subjects receiving second application of the Investigational product. All investigational products must be accounted for, and any discrepancies explained.

The study pharmacist or designated study personnel is responsible for keeping accurate records of the clinical supplies received from the Sponsor, all supplies retained in inventory at the site, and investigational product dispensed to or returned from each subject and should accurately reflect the drug accountability of the investigational product at all times.

If any dispensing errors or discrepancies are discovered, the Sponsor must be notified immediately.

Prior to site closure and at appropriate intervals during the study, a representative from Biorasi or Sponsor will perform Investigational Product accountability and reconciliation. At the end of the study, the Investigator will retain all the original documentation regarding Investigational Product accountability, return, and/or destruction, and copies will be sent to the Sponsor.

With the exception of retention samples, all unused and used investigational product tubes will be retained at the investigative site and must be returned to the Sponsor or its designee for destruction at the end of the study.

